**Table 5.6.1-1: Infusion Reaction Management Guidelines**

NCI CTCAE Grade	Treatment	Premedication at Subsequent Dosing
Grade 1 Mild reaction; infusion interruption not indicated; intervention not indicated	Increase monitoring of vital signs as medically indicated until the subject is deemed medically stable in the opinion of the investigator.	None
Grade 2 Requires infusion interruption but responds promptly to symptomatic treatment (e.g., antihistamines, NSAIDS, narcotics, IV fluids); prophylactic medications indicated for < =24 hrs	Stop Infusion and monitor symptoms. Additional appropriate medical therapy may include but is not limited to: IV fluids Antihistamines NSAIDS Acetaminophen Narcotics	Subject may be premedicated 1.5h ( $\pm$ 30 minutes) prior to infusion of nivolumab with:  Diphenhydramine 50 mg po (or equivalent dose of antihistamine).

	
Increase monitoring of vital signs as medically indicated until the subject is deemed medically stable in the opinion of the investigator.
 
If symptoms resolve within one hour of stopping drug infusion, the infusion may be restarted at 50% of the original infusion rate (e.g., from 100 mL/hr to 50 mL/hr). Otherwise dosing will be held until symptoms resolve and the subject should be premedicated for the next scheduled dose.
 
Subjects who develop Grade 2 toxicity despite adequate premedication should be permanently discontinued from further trial treatment administration.
	Acetaminophen 500-1000 mg po (or equivalent dose of antipyretic).
Grades 3 or 4	
Stop Infusion.
 
Additional appropriate medical therapy may include but is not limited to:
 
 
IV fluids
 
Antihistamines
 
NSAIDS
 
Acetaminophen
 
Narcotics
 
Oxygen
 
Pressors
 
Corticosteroids
 
Epinephrine
 
 
Increase monitoring of vital signs as medically indicated until the subject is deemed medically stable in the opinion of the investigator.
 
Hospitalization may be indicated.
 
Subject is permanently discontinued from further trial treatment administration.
	No subsequent dosing
Appropriate resuscitation equipment should be available in the room and a physician readily available during the period of drug administration		

## 5.7 Subject Withdrawal/Discontinuation Criteria

Subjects are free to withdraw from the study at any time and without penalty or loss of future medical care, or any other benefits to which they are otherwise entitled. Subjects may discontinue study medication for any of the following conditions:

- Dose-limiting or other unacceptable toxicity considered to be related to either study medication;
  - Patients who develop unacceptable toxicity deemed related to CMP-001 but not Nivolumab may continue Nivolumab after CMP-001 discontinuation for duration as defined in **Section 5.2.2.4**.
  - Patients who develop unacceptable toxicity deemed related to Nivolumab but not CMP-001 must discontinue **both CMP-001 and Nivolumab**.
- PD by RECIST (Version 1.1) if accompanied by medically significant clinical deterioration, in the judgment of the Investigator. (Continuation of treatment through suspected pseudo-progression is permitted.);
- If, in the opinion of the Investigator, it is medically necessary;
- Subject withdraws consent for the study (note that subjects who withdraw consent for additional study treatment and procedures will continue to be followed for long-term survival unless they explicitly withdraw consent for any follow-up);
- Subject develops an intercurrent illness or adverse event that precludes further participation, or requires a prohibited concomitant treatment;
- Subject becomes pregnant or begins breastfeeding;

- Subject is lost to follow-up.

Subjects discontinuing study medication earlier than planned or withdrawing from the study should undergo the subsequent End of Treatment (EOT) clinical and laboratory assessments as soon as possible after study medication is stopped and the requisite safety follow-up period of 30 days should also be followed. The reason for withdrawal will be recorded in the electronic case report form (eCRF) and the subject's source medical record. All subjects will continue to be followed every three months after the last CMP-001 treatment for long-term survival follow-up until death, loss to follow-up, or withdrawal of consent for follow-up.

### **5.8 Subject Replacement Strategy**

Subjects who receive at least 1 dose of CMP-001 and nivolumab are evaluable for safety. Patients who complete pre-operative therapy and receive surgery will be evaluable for pathologic response rate and other efficacy endpoints. Patients who did not undergo surgery for reasons of disease progression precluding surgery (rapid disease progression) will be deemed non-evaluable. Non-evaluable subjects may be replaced.

If in the opinion of the treating investigator and treating surgical oncologist in consultation with Principle Investigator, subject's disease is rapidly progressing to the point that window to intervene surgically is narrowing, treatment may be discontinued to permit surgery. These patients are evaluable for pathological response rate and other efficacy endpoints. These patients are eligible to receive CMP-001/nivolumab during "Boost" phase.

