**Figure 4: Management of CMP-001 Associated Cytokine Release-like Syndrome**

#### **5.2.2.8    Changing the selected tumor**

Therapy of a selected lesion generally should continue per protocol unless the tumor is EITHER dramatically responding clinically OR dramatically progressing clinically. Inflammation of the injected tumor is expected following the 2nd and subsequent injections, but should not be mistaken for anti-tumor response or clinical progression.

If during therapy the injected tumor is clearly involuting and shrinking, and if a different eligible accessible tumor is progressing, then the Investigator should change the selection to the progressing tumor, injecting the full dose of CMP-001 into that tumor(s), and continuing to inject the new tumor(s) until EOT (or that tumor shows involution, in which case a third progressing tumor may be selected). If during therapy the injected tumor is clearly involuting and shrinking, and no other lesions are present, CMP-001 may be omitted or injected subcutaneously at the discretion of the treating investigator in consultation with the Principle Investigator.

If during therapy the injected tumor progresses, the treating investigator in consultation with the Principle Investigator may elect to continue therapy or transition to surgery directly. Every effort should be made to complete 7 weeks of perioperative therapy. The decision to proceed with surgery should be made (in consultation with the initial evaluating surgical oncologist) only if there is a danger of the subject being rendered inoperable.

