### **5.10 Surgical Considerations**

The team members will make every effort to comply with the surgical procedures within the time windows allowed in this study protocol. However, under certain circumstances and as discussed between the sub-investigator(s) and the principal investigator, an alteration in the surgical schedule/timing is allowed. These include (but are not limited to) the following:

- A 4 week window between the baseline biopsy and the first dose of nivolumab is allowed.
- The definitive surgery may be a lymphadenectomy or resection of lymphatic metastases as clinically indicated. The definitive surgery may be divided into more than one surgical procedure, scheduled at different time points as clinically/surgically indicated. Under certain circumstances, the definitive surgery may be done after completion of additional therapy (e.g., after the forth dose of nivolumab) or earlier if nivolumab was discontinued due to adverse events or other reasons. Tissue from any of these surgical procedures may be banked under this protocol following the same protocol procedures for tissue handling and banking. The tissue for banking may be digested, frozen or handled in another alternative method as discussed with the investigator.

- If for some reason, the baseline biopsy or definitive surgery could not be completed due to un-anticipated factors such as patient refusal, this will be documented.

**NOTE:** The surgical guidelines are general and may be followed or modified at the discretion of the expert surgical oncologist on the case as clinically indicated and depending on the specifics of the individual surgical case.

For the baseline biopsy required on this study, patients will undergo a core needle, punch biopsy, open surgical biopsy, or other technique at the discretion of the sub-investigator/investigator. The choice of specific surgical technique will be at the discretion of the surgeon or medical oncologist and actual techniques will be the same as those used as therapeutically or diagnostically indicated to surgically treat or confirm the clinical suspicion of recurrent or metastatic disease in any patient undergoing conventional evaluation and treatment (standard of care) within 21 days (preferred; and up to 4 weeks) prior to entry to the study.

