### 8.3 Sample Size

Several of the agents being utilized in the melanoma armamentarium have been evaluated in the neoadjuvant context including: HDI (Moschos et al. 2006), ipilimumab (Tarihini et al. 2014), pembrolizumab (Forde et al. 2018) and nivolumab/ipilimumab combination (Blank et al. 2018; Amaria et al. 2018). In earlier studies, response was typically assessed using chemotherapy criteria and reported as pathologic complete response (pCR) rates. Cognizant of the different mechanism of action of immuno-oncologic agents, more recent studies have utilized alternative means of assessing response using novel immuno-oncologic agent-specific criteria (major pathologic response or MPR rate) as delineated in **Section 8.4.** In the latter studies, MPR rates reported with PD-1 inhibitors range from 28% (Nivolumab, melanoma) to 45% (Nivolumab/Ipilimumab, melanoma) (Huang et al. 2019; Blank et al. 2018; Amaria et al. 2018).

However, the PD-1/CMP-001 combination has not been evaluated in the neoadjuvant setting and the MPR rate for this combination is unknown. To balance efficacy while minimizing exposure of patients to a potentially ineffective combination, we utilize Simon's minimax two-stage design with MPR as the primary endpoint.

In this study, we will test the null hypothesis of 28% MPR versus the alternative hypothesis of 55% MPR. In the 1st stage, we will enroll 14 evaluable patients (defined in **Section 5.8**). If we see at least 5/14 major pathologic responses, we will enroll a further 16 patients to the 2nd stage. The combination will be considered worthy of further evaluation if ≥13 responses are observed in both stages in 30 evaluable patients. The Simon's **minimax** two-stage design and sample size of 30 evaluable patients provides a type I error rate of 5%, with a power of 0.91. Allowing for 10% drop out rate, we set a total sample size of 33 patients.

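### Section 5.8 does not say whether patients who stop Prime therapy early for toxicity and are then resected count for MPR, so they can be left out of both Simon decisions and replaced

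*Combined protocol and SAP*

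**What the plan says.** Section 5.8 (Subject Replacement Strategy) sets a two-part condition: "Patients who complete pre-operative therapy and receive surgery will be evaluable for pathologic response rate and other efficacy endpoints". It then describes patients whose treatment is cut short because rapid progression is closing the surgical window, and says of them: "These patients are evaluable for pathological response rate and other efficacy endpoints". The one group it expressly calls non-evaluable is patients whose progression ruled out surgery. Non-evaluable subjects may be replaced, at the study team's option.

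Section 5.10 (Surgical Considerations) allows definitive surgery "earlier if nivolumab was discontinued due to adverse events or other reasons". Section 5.7 provides for stopping both drugs when toxicity is attributed to nivolumab.

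The design in Section 8.3 rests on this definition: "we will enroll 14 evaluable patients" in stage 1, with a reference back to 5.8. "If we see at least 5/14 major pathologic responses, we will enroll a further 16 patients", and the combination is judged worth pursuing "if ≥13 responses are observed in both stages in 30 evaluable patients". Section 8.4 also defines an evaluable patient only by pointing to 5.8, yet it has residual tumor determined in each resection specimen.

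**The concern.** A patient who stops both drugs early for toxicity and is then resected has a specimen and an MPR result. That patient did not complete pre-operative therapy in the ordinary sense and was not stopped for progression, so 5.8 gives no ground for counting them. Whether a resected patient counts then depends on why therapy was shortened, not on whether MPR can be read. A patient stopped early for progression counts; a patient with the same exposure stopped for toxicity may not.

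The primary endpoint, both Simon decisions and the reported MPR rate all use this set. A consistent exclusion shifts the estimate toward patients who tolerate the Prime phase or progress during it. A case-by-case choice, made with pathology in hand, would allow selection on the outcome. The plan does not say who decides evaluability or when.

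**Working it through.** **Inputs.** Section 8.3: "we will test the null hypothesis of 28% MPR versus the alternative hypothesis of 55% MPR"; continue with at least 5 of 14; succeed with at least 13 of 30; stated type I error 5% and power 0.91; total 33 after a 10% dropout allowance. The documents do not give the share of resected patients who stop early or their MPR rate. I assume a share of 5% to 20% and an MPR rate of 0% to 55%.

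**Step 1: the plan's own figures.** The exact success probability at MPR rate p is

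P(p) = Σ (x = 5 to 14) C(14, x) p^x (1 − p)^(14 − x) × Pr[Bin(16, p) ≥ 13 − x].

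This gives P(0.28) = 0.0470 and P(0.55) = 0.907, which agree with the stated 5% and 0.91. The total of 33 is 30 × 1.10.

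**Step 2: consistent exclusion.** Hold the true MPR rate among all resected patients at 28%. Let a share t stop early with MPR rate m, and let all of them be left out and replaced until 30 are evaluable. The rule then runs at (0.28 − t·m)/(1 − t). For t = 0.10 and m = 0 this is 0.28/0.90 = 0.311. For t = 0.10 and m = 0.55 it is (0.28 − 0.055)/0.90 = 0.250.

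Type I error, relative to all resected patients:

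| Share t | m = 0% | m = 10% | m = 28% | m = 55% |
|---|---|---|---|---|
| 5% | 6.8% | 6.0% | 4.7% | 3.2% |
| 10% | 9.8% | 7.7% | 4.7% | 2.0% |
| 20% | 20.3% | 13.0% | 4.7% | 0.5% |

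Reaching 30 evaluable needs about 30/0.90 = 33.3 resected patients at a 10% share and 30/0.80 = 37.5 at 20%. The 20% row therefore exceeds the stated total of 33.

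**Step 3: worst-case selection.** Suppose early stoppers with MPR are kept and those without are replaced. For an early-stop share q, with the same 28% rate in stoppers and completers, the effective null rate is 0.28/(0.28 + 0.72 × (1 − q)). The expected number of replacements needed to reach 30 is 30 × 0.72q/(1 − 0.72q). The capped column is an exact recursion that allows at most 33 − 30 = 3 replacements; any later non-responding stopper is counted.

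| q | Effective null rate | Type I error, no cap | Expected replacements | Type I error, at most 3 replaced |
|---|---|---|---|---|
| 5% | 0.28/0.964 = 29.0% | 6.1% | 1.1 | 6.1% |
| 10% | 0.28/0.928 = 30.2% | 8.0% | 2.3 | 7.5% |
| 20% | 0.28/0.856 = 32.7% | 13.6% | 5.0 | 9.3% |

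**Step 4: effect on a reported rate.** Take 13/30 = 43.3% (exact 95% CI 25.5% to 62.6%). If three resected early stoppers were left out, the rate in all resected patients is 13/33 = 39.4% if none responded and 16/33 = 48.5% if all did.

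**The case against.** The strongest reply is that 5.8 never calls these patients non-evaluable. The label is attached only to patients whose progression prevented surgery, so a reader who infers that resected toxicity stoppers are excluded by rule goes further than the text. That stands: the defect is a gap. But a gap in the definition used by 8.3 and 8.4 leaves the choice open, and no other section closes it.

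A second reply is that completing therapy can reasonably mean completing the Prime period with permitted modifications. Section 5.2.1.4 does not make up missed Prime nivolumab doses. Sections 5.2.2.4 and 5.7 let nivolumab continue after CMP-001 stops. When the injected tumor is shrinking and no other lesion is present, Section 5.2.2.8 says "CMP-001 may be omitted or injected subcutaneously at the discretion of the treating investigator". It is tempting to add that last group to those excluded, but the omission is allowed by protocol and the text does not support counting it as non-completion. The clear cases are narrower: patients who stop the regimen early and then have surgery.

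A third reply is that the larger error rates depend on assumptions. That also stands. Selective replacement is an upper bound, not a prediction, and the documents do not say that replacement is decided after pathology; they are silent on timing. There are partial safeguards: the reason for withdrawal is recorded, and two pathologists read slides blinded to clinical information. Neither fixes who is in the analysis set. The cap of three follows from the total of 33; Section 5.2 speaks of up to 40 evaluable patients, which is not reconciled with 33 and would loosen the cap.

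Finally, short exposure may be thought not to test the regimen, since the primary objective refers to 7 weeks of treatment. Section 5.8 already counts short-exposure patients stopped for progression, so exposure alone is not its criterion.

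**Conclusion.** The point holds as a gap in the evaluability definition that should be closed. Resected patients whose Prime therapy was shortened for toxicity or other non-progression reasons fall outside the 5.8 definition, have a readable specimen, and can be left out and replaced with no requirement to decide before the result is known.

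A reader might infer that the design's type I error is wrong or necessarily inflated. The documents do not support that: the stated figures reproduce, and under consistent exclusion the error can rise, stay at 4.7% or fall, depending on an MPR rate that nobody has stated. At a 10% share the range is 2.0% to 9.8% for MPR rates of 55% down to 0%. Deliberate selection would give about 6% to 9% within the planned 33 patients, and 13.6% at most without the cap. All of this rests on assumed early-stop shares of 5% to 20%. Patients who never reach surgery because of progression are a separate matter.

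**What to change.** In Section 5.8, state that every patient who received at least one dose of both CMP-001 and nivolumab and underwent resection is evaluable for MPR, whatever the reason Prime therapy was shortened, and is not replaced. Requiring both drugs matches the safety set in 5.8. A threshold of one dose of either drug would admit a patient given only the Week 1 subcutaneous CMP-001 dose, who would then count for efficacy but not for safety.

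In Section 8.4, add MPR in patients who completed Prime therapy, with protocol-allowed omissions counted as completion, as a sensitivity analysis.

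The cost is one sentence in 5.8 and one line in 8.4. The design stays at 14 + 16 = 30 evaluable, with type I error 0.047 and power 0.907, and no treatment or stopping rule is affected. The downside is small: some patients with shortened exposure enter the primary set, as 5.8 already accepts for those stopped for progression.

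### Patients whose progression prevents surgery are dropped from the primary MPR set and may be replaced, so the MPR rate overstates the rate among treated patients whenever this happens

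*Combined protocol and SAP*

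**What the plan says.** Section 5.8 makes patients evaluable for pathologic response if they finish pre-operative therapy and have surgery. For those who progress too far for an operation it says: "Patients who did not undergo surgery for reasons of disease progression precluding surgery (rapid disease progression) will be deemed non-evaluable". It adds: "Non-evaluable subjects may be replaced". Patients taken to surgery early because of rapid progression are treated differently: "These patients are evaluable for pathological response rate and other efficacy endpoints".

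Section 8.3 counts both stages in evaluable patients and refers to Section 5.8 for the definition. Accrual continues on this condition: "If we see at least 5/14 major pathologic responses". The final rule is: "The combination will be considered worthy of further evaluation if ≥13 responses are observed in both stages in 30 evaluable patients". The claimed operating characteristics are: "two-stage design and sample size of 30 evaluable patients provides a type I error rate of 5%, with a power of 0.91". The null rate is 28% and the alternative 55%. The 28% is taken from cited reports, without saying whether their denominator was treated or resected patients. On enrolment: "Allowing for 10% drop out rate, we set a total sample size of 33 patients".

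Section 8.4 sends the reader back to Section 5.8 for the evaluable set. It defines MPR by the residual tumor in the post-therapy specimen and plans the MPR rate with an exact 95% interval. Nowhere does the plan score a treated patient without a specimen as non-MPR, or plan an MPR analysis of all treated patients.

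**The concern.** The exclusion depends on what happens after treatment starts, and it acts in one direction only. A patient whose disease became inoperable has no specimen and so cannot contribute an MPR. Dropping that patient shrinks the denominator and leaves the numerator alone; replacement then offers another chance of a response. Progressors who still reach surgery are counted, so it is the worst courses that leave the data.

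The trial has one arm, so the MPR rate is itself the result, and no control group shares the bias. The primary objective in Section 3.1 concerns patients given the combination, not only those who reach surgery. The same denominator governs the stage 1 futility check, which becomes easier to pass relative to the rate among treated patients.

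**Working it through.** **Inputs.** From Section 8.3: n1 = 14, continue at 5 or more; n = 30, success at 13 or more; p0 = 0.28, p1 = 0.55; 33 patients in total. The share f of treated patients whose progression prevents surgery is not in the documents. It is an assumption here, shown from 1% to 10%.

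**1. The plan's own figures.** With exact binomial probabilities,

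P(success | p) = Σ (x = 5 to 14) P[Bin(14, p) = x] × P[Bin(16, p) ≥ 13 − x].

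This gives 0.0470 at p = 0.28 and 0.9073 at p = 0.55. The stated 5% (as a ceiling) and 0.91 are correct for evaluable patients.

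**2. Effect on the estimate.** This step needs no assumption about the meaning of 28%. Take 13 responses in 30 evaluable patients, with k progressors excluded and replaced. The rate among these treated patients is 13/(30 + k).

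| k | Rate | Exact 95% CI |
|---|---|---|
| 0 | 13/30 = 43.3% | 25.5% to 62.6% |
| 1 | 13/31 = 41.9% | 24.5% to 60.9% |
| 2 | 13/32 = 40.6% | 23.7% to 59.4% |
| 3 | 13/33 = 39.4% | 22.9% to 57.9% |

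At stage 1, 5/14 = 35.7% with one replaced progressor is 5/15 = 33.3%.

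**3. Chance that the rule is used at all.** Among 33 treated patients, P(at least one loss) = 1 − (1 − f)^33. For f = 1%, 2%, 3%, 5% and 10% this is 28%, 49%, 63%, 82% and 97%.

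**4. Error rates, only if 28% is an all-treated rate.** An all-treated rate of 0.28 becomes 0.28/(1 − f) among evaluable patients; at f = 5%, 0.28/0.95 = 0.2947. With unlimited replacement, that value goes into the formula of step 1. With at most 33 treated, an exact recursion over patients treated, patients evaluable and responses was used. It was run twice: once requiring all 30 evaluable patients, and once letting 13 responses suffice if fewer than 30 are reached.

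| f | Type I error, unlimited | Cap 33, 30 required | Cap 33, 13 responses suffice | P(pass stage 1) |
|---|---|---|---|---|
| 0 | 0.0470 | 0.0470 | 0.0470 | 0.351 |
| 1% | 0.0506 | 0.0506 | 0.0506 | 0.360 |
| 2% | 0.0545 | 0.0543 | 0.0545 | 0.369 |
| 3% | 0.0587 | 0.0577 | 0.0585 | 0.379 |
| 5% | 0.0681 | 0.0626 | 0.0666 | 0.399 |
| 10% | 0.0985 | 0.0568 | 0.0838 | 0.452 |

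The third column falls at f = 10% because the chance of obtaining fewer than 30 evaluable patients from 33 is then 0.42. The cap is itself uncertain, since Section 5.2 allows up to 40 evaluable patients. A limit of 40 treated gives the unlimited figures to within 0.0002.

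**5. If 28% is a resected-patient rate.** The null and the analysis set then match and type I error stays at 0.0470. Step 2 still applies.

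**The case against.** The strongest reply is that the error-rate harm depends on source studies that the documents do not describe. If 28% came from resected patients, the decision rule is sound. That is right, and for this reason step 4 is conditional.

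What remains without that condition is modest: at most 3.9 points (43.3% to 39.4%) for three exclusions, inside an interval about 37 points wide, and nothing if no one is excluded. This also stands. But the shift is systematic, whereas the interval describes sampling error only, and nothing in the planned analysis would reveal the shift.

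The protocol also narrows the group. Potential resectability must be established at baseline (Section 5.1.2), surgery may be brought forward if operability is threatened (Section 5.2.2.8), and those patients stay evaluable. So f may be small, and no document supports the 10% value; the 10% in Section 8.3 is general dropout. The problem is narrowed but not removed, and Section 5.8 has a rule for exactly these patients.

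The protocol recognises pseudo-progression, so calling every excluded patient a biological failure would go too far. It is enough that none can be an MPR under Section 8.4.

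Finally, an all-treated sensitivity analysis would disclose the bias at less cost. It would still leave both decisions and the headline rate on a set selected by outcome.

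**Conclusion.** The concern holds, and the rule should be corrected before the primary analysis. Followed as written, the plan removes patients who cannot be responders from the denominator of its primary endpoint. The upward direction is certain once at least one such patient and at least one MPR occur. At the success boundary the overstatement is 1.4, 2.7 or 3.9 percentage points for one, two or three replaced progressors.

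The stated type I error and power are correct for evaluable patients. Type I error is inflated only if 28% describes all treated patients, and then by an amount that depends on the assumed f: 5.1% at f = 1%, and 6.3% to 6.8% at f = 5%, depending on the enrolment cap. Section 8.3 does not settle which population 28% describes.

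**What to change.** In Sections 5.8 and 8.4, make the primary MPR set all patients who start study treatment, the set Section 8.2 already uses for safety. Section 5.8 describes the safety set differently (at least one dose of each drug), so the two should be aligned. Count patients with no resection specimen because of progression, toxicity or death as non-MPR within the 14 and the 30, without replacement. Allow replacement only for withdrawal unrelated to disease or treatment. Report the resected-only rate as supportive. Keep 5/14 and 13/30.

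In Section 8.3, establish from the source studies which population 28% and 55% describe, state it, and restate power if 55% is a resected-patient rate. Do not lower the null rate by an assumed f.

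**Cost.** Wording changes only, with no extra patients and no change to care. The reported MPR rate may be lower, and the three spare places would cover unrelated withdrawals only. If 28% and 55% are all-treated rates, type I error is 0.0470 and power 0.907. If they are resected-patient rates, the all-treated rates are 0.28(1 − f) and 0.55(1 − f), and the step 1 formula gives:

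| f | Type I error | Power |
|---|---|---|
| 1% | 0.0436 | 0.897 |
| 2% | 0.0404 | 0.887 |
| 3% | 0.0374 | 0.876 |
| 5% | 0.0319 | 0.850 |
| 10% | 0.0208 | 0.77 |

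The kept rule is then stricter than planned, which is why the populations behind both rates must be stated.
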